treatment, concerns about logistically attending sessions, and appealing features of the treatment). Step five will include revising the treatment procedures and content based on the results from each cohort of development testing. Table 2 provides an overview of the timeline for Study 1.

Statistical Considerations. The primary goal of Study 1 is to develop MBRP-SA. Qualitative analysis of focus group will be the primary form of evaluation. The focus group will be audio-recorded and verbatim transcripts created for content analysis.¹⁵⁰ Using hand coding, the goal will be to identify key themes/textual units related to mindfulness and response to the treatment. Results from the qualitative interviews will be analyzed using the interview transcripts and content analysis. Content analysis will be conducted using an “intuitive” or “immersion/crystallizing” analysis plan, whereby the researcher reviews all data and pulls out those aspects most relevant to the research questions.¹⁵¹ The research team will identify key themes as they read through the interview transcripts. Descriptive statistics of quantitative measures will supplement the qualitative analysis. These may provide information for identifying aspects of implementation that require change prior to the feasibility study (Study 2).

Aim 2.

*Note: All procedures reported for Aim 2 will be conducted remotely, primarily via zoom and phone calls (but also via mailouts, emails, and text messages as appropriate). Group treatment sessions (MBRP-SA and CBT) will be conducted via zoom.

Project Overview. The primary goal of Study 2 is to measure benchmarks regarding the feasibility and acceptability of the MBRP-SA protocol created in Study 1. Participants (N=64) will be randomized to either MBRP-SA or CBT and tracked from 5 weeks pre-quit through 16 weeks post-quit. The first follow-up appointment will be a phone call scheduled at 8 weeks post-cessation (± 5 days). The second follow-up appointment will be a phone call scheduled at 16 weeks post-cessation (± 5 days). Table 4 provides a timeline of all procedures and assessments. Details are presented in the subsequent sections. Administering the battery of assessments below according to this timeline mimics the procedures for a future, large-scale R01 efficacy trial and will allow for the evaluation of feasibility for completing all procedures.

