^a = data collected during phone call (vs REDCap)

Phone Orientation Visit. Study personnel will call the participant at their scheduled session time and provide a detailed description of the study and obtain verbal consent. A copy of the informed consent and a PowerPoint describing the study in detail will be mailed and/or emailed to participants before the orientation session. If the participant decided to consent to the study, a series of self-report questionnaires to complete will be emailed to them (see Aim 3 below). Individuals who are ineligible or decline to participate will receive self-help materials and referrals for smoking cessation and alcohol use programs.

Zoom Orientation Visit. Consented participants will be scheduled for a group Zoom Orientation session one week before the first treatment session. Prior to the visit, participants will be provided a packet of instructions on how to access and navigate the video-conferencing app, Zoom, and additional materials related to the study (e.g. session handouts, welcome materials). Tablets, webcams, and/or microphones will be provided to participants on an as-needed basis. This orientation session will take place via Zoom. During this session, participants will be provided with a training on how to use video-conferencing app and will discuss the other relevant materials sent to participants in preparation for the first treatment visit. Prior to all Zoom visits in the study, participants will join a waiting room before they are admitted to the group, where they will see banners with reminders about sessions content, privacy standards, etc. This procedure will be followed for all treatment sessions as well as the Zoom Orientation session.

Randomization. Three stratification variables will be included: gender (men vs women), race/ethnicity (non-Hispanic White vs Other), and smoking rate (20+ cigarettes per day [CPD] vs less than 20). Within these 8 cells, eligible participants will be assigned to the two treatments using balanced-permuted block randomization with a block size of 4.

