To ensure participant confidentiality, no unique identifiers will be recorded into the dataset to be analyzed. Data will be collected via REDCap. The entered and reviewed data will be transferred monthly to a SPSS database.¹⁷⁴

Sample Size. Randomizing 64 participants to MBRP-SA and CBT will provide sufficient data for assessing feasibility of the RCT, based on existing recommendations in the literature for sample size estimates in feasibility studies.^{175,176} A full set of statistical analyses focusing on treatment differences will be performed as part of the feasibility assessment. However, the sample size will not be sufficient for detecting treatment differences for anything less than large effect sizes (e.g., Cohen's $d \geq .72$) for simple, two-group comparisons of a continuous variable with $\alpha=.05$, power $\geq .80$, and a two-tailed test. Binary variables assessed under the same testing conditions would require an $OR \geq 5.95$.

Data Analysis Overview. Analyses will be conducted with SPSS and SAS version 9.4¹⁷⁴ and Mplus Version 7.¹⁷⁷ Descriptive statistics of demographics, smoking history, and alcohol history variables will be calculated and group comparisons will be performed. Descriptive statistics of all study measures (i.e., proximal and distal measures of alcohol use and smoking) will be calculated. Although underpowered to detect small- or medium sized sex differences, all analyses will examine sex as a covariate. Furthermore, analyses will include treatment group (i.e., each subset of participants who are treated with MBRP-SA or CBT together) when the intraclass correlation coefficient is > 0.10 .

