Aim 2 - Evaluate benchmarks regarding feasibility and acceptability. Feasibility will be assessed by the multiple indices described in Table 5. Each index will either be compared to published norms (e.g., CSQ) or our prior experience with clinical trials. We expect to recruit adequate numbers of eligible participants during the study timeframe with efficient cost expenditures, retain at least 80% through the end of treatment, and retain at least 70% through the end of the study. Treatment acceptance and satisfaction are expected to be 80% or higher, and participants are expected to comply with treatment requirements. The team will determine whether corrective actions for future studies are needed when an index suggests underperformance. Evaluation of all indices will inform and guide modification prior to the proposal of a full-scale RCT.

Aim 3 - Collect and examine descriptive data on proximal and distal variables associated with alcohol use and smoking. Descriptive statistics of proximal measures (e.g., negative affect, self-efficacy) will be presented in figures to review change over time and treatment differences. Generalized estimating equations (GEE) will be used to fit population-averaged models with the main variables of treatment, time, and their interaction. An AR(1) working correlation matrix will be used with $r=.70$. Covariates and potential confounding variables will be included, as warranted. This approach preserves data for analysis by avoiding listwise deletion of observations when at least one dependent variable was observed. Qualitative analyses (e.g., thematic analysis) may also be conducted on aspects of the treatment process.

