A similar approach to analysis will be taken for the primary outcomes (the distal measures). TLFB will be used to derive a measure of heavy alcohol use and the 7-day point prevalence will be created for smoking abstinence at five targeted 1-week periods prior to a session: start of treatment (week -4), quit date (week 0), end of treatment (week +3), and two follow-ups (week +8 and week +16). Descriptive statistics will be presented in figures. GEE with an AR(1) working correlation matrix ($r=.60$) will be used to assess the effects of treatment, time (-4, 0, +3, +8, +16), and their interaction on the primary outcome measures. Means, percentages, and 95% confidence intervals will provide useful guidance as we determine sample sizes for a full-scale RCT. There is not adequate power to detect small- to medium-sized treatment group differences given the sample size. However, we would interpret any within-subject decreases in the number of heavy drinking days from pre- to post-treatment and/or any within-subject increases in smoking abstinence as evidence that the MBRP-SA intervention may be beneficial for these two problematic health behaviors. Given the small sample size, these changes are not likely to be significant. However, sample means and standard deviations will provide valuable data for

estimating sample size in a large-scale RCT. Changes in craving, self-efficacy, and general use of alcohol and smoking will also be examined as proximal outcomes that will also inform the development of a large-scale trial.

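### The rule to include therapy group does not say how; entered as a covariate, group aliases the treatment coefficient and gives the treatment-by-time test essentially no protection

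*Combined protocol and SAP*

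**What the plan says.** All references are to the combined protocol and SAP.

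- **Data Analysis Overview.** One sentence says that sex will be examined as a covariate in all analyses. The next says that "analyses will include treatment group (i.e., each subset of participants who are treated with MBRP-SA or CBT together" when the ICC is above 0.10. The role of group in the model is not given.
- **Aim 3 analysis, proximal measures.** "Generalized estimating equations (GEE) will be used to fit population-averaged models with the main variables of treatment, time, and their interaction". The working correlation is AR(1) with r = .70.
- **Aim 3 analysis, distal measures.** The same approach with r = .60 is used "to assess the effects of treatment, time (-4, 0, +3, +8, +16), and their interaction on the primary outcome measures". The outcomes are heavy drinking and binary 7-day abstinence. Neither paragraph has a group term, a group-level clustering unit or a small-sample correction.
- **Allocation.** "Participants (N=64) will be randomized to either MBRP-SA or CBT", and individuals are "assigned to the two treatments using balanced-permuted block randomization with a block size of 4" within eight strata. They are then treated in arm-specific groups of 8-10 (MBRP Overview; MBRP-SA and CBT), with different therapists in each arm (Selection Criteria).
- **Selection Criteria** also promises that therapist effects will be evaluated later in the text. No model follows.

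**The concern.** Participants are randomized one by one but treated in about 3-4 groups per arm, and members of a group can come to resemble each other. The ICC rule shows that the authors want to allow for this. The rule sits directly after the sentence on sex as a covariate, and the GEE has no random effects, so an analyst would most naturally add group as another covariate.

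That step does two things the authors would not want. Group is nested in arm, so the arm indicator equals the sum of its own group indicators and the treatment coefficient has no separate meaning. And a group term that is constant over time cannot absorb a group effect that appears only once sessions begin, which is the form of clustering most relevant to a change from week -4.

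The intervals are at stake. The Aim 3 text says that the means, percentages and 95% confidence intervals will guide the sample size of the full-scale trial. Intervals that ignore group are too narrow whatever the power of this study.

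**Working it through.** **1. The plan's own figure.** The Sample Size paragraph gives "large effect sizes (e.g., Cohen's $d \geq .72" for 64 participants, two-sided alpha .05 and power of at least .80. Per arm, n = 2(1.96 + 0.84)²/0.72² = 30.3, so 31. With 32 per arm, power is Φ(0.72 × √16 − 1.96) = Φ(0.92) = .82 (.81 with the t distribution). The figure reproduces, for independent observations. The odds ratio of 5.95 reproduces (power .80) if the control rate is 10%, which the plan does not state.

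**2. Aliasing.** Assume 8 groups of 8, four per arm. Intercept + arm + 7 group indicators make 9 columns, of rank 8. With time and treatment-by-time added there are 17 columns of rank 16, and dropping the treatment column leaves the rank at 16. If software drops a redundant group column, the printed treatment coefficient can be a contrast of two reference groups. For 8 v 8 the noncentrality is 0.72 × √(8/2) = 1.44, giving 29% power on 56 df, against 81% for 32 v 32.

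The average of group means in one arm minus the other remains estimable, but it treats groups as fixed. With a constant group ICC of .10 (600 simulated trials), its type I error was 28.7%. The treatment effect averaged over visits without group indicators had 22.2%.

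**3. Treatment-by-time, group effect arising after baseline.** Let ρ be the post-baseline ICC and r the participant's correlation between week -4 and the later visit.

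- ICC of the change: ρc = ρ / [2(1 − r)(1 − ρ) + ρ]
- Design effect for groups of 8: D = 1 + 7ρc
- Type I error when groups are ignored: 2Φ(−1.96/√D)

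Two values of r bracket the plan's AR(1) with r = .60: .6 for adjacent visits, and .6⁴ = .13 for week -4 to week +16 (four steps).

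| ρ (assumed) | r = .6: ρc, D, type I | r = .13: ρc, D, type I |
|---|---|---|
| .05 | .062, 1.43, 10% | .029, 1.21, 7% |
| .10 | .122, 1.85, 15% | .060, 1.42, 10% |
| .15 | .181, 2.27, 19% | .092, 1.64, 13% |

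Simulation gives 7-10%, 10-14% and 12-19%, within about a point of the formula. A comparison of the eight group means on 6 df holds about 5%.

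**4. Do group indicators help?** Type I error of the week-16-by-treatment test in the AR(1) GEE with participant-level robust variance, 600 trials per row (Monte Carlo error about 1-2 points):

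| Scenario (identity link) | Without group | With group |
|---|---|---|
| Constant group effect, ICC .10 | 5.2% | 5.2% |
| Post-baseline, ICC .10, complete data | 12.8% | 12.8% |
| Post-baseline, ICC .20, complete data | 15.7% | 15.7% |
| Post-baseline, ICC .10, 70% retention | 8.7% | 8.7% |
| Post-baseline, ICC .20, 70% retention | 14.5% | 16.0% |

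For a binary outcome with logit link (two visits, latent ICC about .09 and .17), the rates were 10.2% v 8.8% and 15.0% v 14.8% with complete data, and 7.3% v 7.2% and 10.4% v 11.2% with 30% dropout.

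**5. Group as the clustering unit.** With participant-level AR(1) kept, the robust variance summed by therapy group and scaled by 8/7, and a t reference on 6 df, type I error was 5.2-7.0% in all six scenarios run.

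**The case against.** Several stronger readings are tempting, and the documents do not support them.

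- *The rule cannot work in a GEE.* The text says only that group is included. Clustering on group is still a GEE, and step 5 shows that it performs acceptably with 6 df. SAS and Mplus, both named in the plan, can also fit a random group effect. The sound criticism is that the role is unspecified and the most natural reading fails.
- *The treatment effect becomes inestimable.* Only the coefficient is aliased. A contrast of group averages survives, though poorly calibrated. The 8 v 8 comparison misleads only someone who reads the default coefficient as the treatment effect. Because week -4 is in the model, much of the interest lies in treatment-by-time anyway.
- *Adding group changes nothing at all.* That is an identity only for an identity link with complete data. The plan expects 80% and 70% retention and has a binary outcome. There the test statistics do move, but the error rates stay close.
- *Clustering must arise after baseline.* This is plausible, not stated. Flexible scheduling of sessions could make groups differ from the start, and a constant group effect leaves the interaction near nominal.

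It is also fair that ICCs of .05 and .10 do not exceed the trigger, although a sample estimate could exceed it when the true value does not. Finally, Study 2's primary outcomes are the Table 5 benchmarks, and Aim 3 is declared underpowered. That lowers the severity. It does not excuse intervals that are too narrow for the planning use the text gives them.

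**Conclusion.** The concern holds as a specification gap with a harmful default. On the covariate reading, the treatment coefficient is aliased with group, and the arm contrast that remains has 28.7% type I error at a constant ICC of .10. The treatment-by-time test is essentially unprotected when group effects begin after baseline: about 7-10%, 10-14% and 12-19% at ICC .05, .10 and .15. When group effects are constant over time, the interaction is near nominal (5.2%) and the main effect is inflated instead. Clustering on group works only with a small-sample reference, which the plan does not state.

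These sizes rest on assumptions: 8 groups of 8, the ICC values, the timing of the group effect, and a correlation between .13 and .6. Severity is moderate: no benchmark decision depends on these tests, but the intervals feed the design of the full-scale trial.

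**What to change.** In the Data Analysis Overview, replace the instruction to include treatment group with wording such as this:

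*Therapy group is never entered as a fixed covariate. Between-arm contrasts account for therapy group nested in arm and allow group effects to differ after baseline. This is done either by a mixed model with a random therapy-group effect and small-sample degrees of freedom, or by GEE with robust variance clustered on therapy group and a t reference on the number of groups minus 2. For abstinence, or if the group variance is estimated as zero, a group-level comparison on the same degrees of freedom is used.*

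Write the degrees of freedom as a rule, not a number: 6-8 groups give 4-6 df. In the GEE version, state that AR(1) applies to visits within a participant, not across members of a group. Repeat the choice in both Aim 3 analysis paragraphs.

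The cost is a change of wording and procedure in software already named, plus wider intervals. For a single post-baseline comparison with 8 groups of 8, the widening is √(1 + 7 × .05) = 1.16 at ICC .05 and √(1 + 7 × .10) = 1.30 at ICC .10. Each is multiplied by 2.447/1.96 = 1.25 for 6 df, giving about 1.45 and 1.63 times the present width.

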2. STUDY DESIGN AND METHODS

Aim 1.

Project Overview. The primary goal of Aim 1 is to modify an existing treatment – MBRP – to include a focus on smoking cessation and reducing alcohol use (MBRP-SA). In this section we include a description of MBRP and the proposed modifications to the original protocol to include a focus on smoking abstinence and reduced alcohol use (Study 1).

MBRP Overview. MBRP was designed to target key components in the relapse prevention process, with a specific focus on negative mood and craving. Principles of the treatment were derived MBRP¹³⁹ and MBCT.¹⁴⁰ MBRP-SA will use the same session structure as MBRP, with 8 weekly in-person group sessions that are 2 hours each. Group sizes for MBRP-SA will be 8-10 participants. The current study will follow the existing treatment manual for MBRP,¹⁴¹ with necessary modifications as described in the following section. The core aims of MBRP are to aid individuals in developing an awareness of the present moment and the ability to shift attention (i.e., the opposite of being on autopilot) and to increase tolerance of emotional, cognitive, and physical states that are unpleasant or negative. The mindfulness practices within MBRP teach individuals how to hone these skills, which allows them to better manage substance use craving when it does occur. Examples of these practices include mindfulness meditation, mindful movement, body scan, and awareness of the senses.

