Treatment Overview. All participants will receive nicotine replacement therapy (NRT) and either MBRP-SA or CBT. Table 4 provides an overview of all treatment and follow-up visits.

NRT. The nicotine transdermal patch is the most widely used pharmacotherapy and the Treating Tobacco Dependence Clinical Practice Guideline has identified it as frontline therapy.¹⁴² The patch is safe, tolerable, and available over-the-counter. Patch therapy for participants who smoke >10 CPD will consist of 6 weeks of 21 mg patches and 2 weeks of 14 mg patches. Patch therapy for participants who smoke 5-10 CPD will consist of 6 weeks of 14 mg patches and 2 weeks of 7 mg patches. Patch dispensation will occur at weekly treatment visits. Participants receive only the number of patches needed to last until the next visit plus several extra patches should one fall off, become torn, etc, or should the visit be delayed. Based on our previous research, compliance is improved when participants are provided with only enough patches to last until the subsequent visit. A reduction in dosage or cessation of the patch regimen will be implemented for any participants who show signs of being on too high of a dose, which is expected for very few participants since blood nicotine levels are usually much lower on the patch than while smoking. Note that for Aim 2, patches will be mailed each week.

MBRP-SA and CBT. MBRP-SA was already described above. CBT is a well-established and commonly used treatment for substance use behaviors that primarily utilizes a problem solving and coping skills approach rooted in relapse prevention theory,¹⁵² combined with standards from the Guideline.¹⁴² Session content will generally follow the manual used in the original MBRP RCT⁶⁴, the MBAT RCT⁵⁸, and standards from the Guideline (e.g., setting a quit date, providing NRT).¹⁴² CBT will consist of 8 sessions (2 hours each), with 8-10 participants in each group. Thus, participants in both MBRP-SA and CBT will be matched on treatment contact time. All treatment activities focus on promoting/maintaining smoking abstinence and reducing drinking, with specific treatment objectives for each session. Participants will receive weekly emails that outline the group session as well as include relevant links and attached handouts for their review. Participants will also receive referrals for mental health and substance use at the end of treatment.

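### Therapy group is modelled only if its estimated ICC exceeds 0.10, a screen that 6 to 8 groups cannot support; Aim 3 between-arm error is then roughly 4–10%, depending on choices the plan leaves open

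*Combined protocol and SAP*

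**What the plan says.** All of this is in section 2 of the combined protocol and SAP.

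- Aim 2, Project Overview: "Participants (N=64) will be randomized to either MBRP-SA or CBT". The same paragraph says the assessment timetable "mimics the procedures for a future, large-scale R01 efficacy trial".
- Both arms are group-delivered. MBRP Overview: "Group sizes for MBRP-SA will be 8-10 participants". The paragraph on MBRP-SA and CBT describes CBT "with 8-10 participants in each group".
- Part G, Data Analysis Overview, defines the clustering unit as "each subset of participants who are treated with MBRP-SA or CBT together" and brings it into the analyses "when the intraclass correlation coefficient is > 0.10".
- Part G, Sample Size: "A full set of statistical analyses focusing on treatment differences will be performed as part of the feasibility assessment". It concedes that "the sample size will not be sufficient for detecting treatment differences for anything less than large effect sizes", and puts the detectable difference at d of .72 or more.
- Part G, Aim 3, specifies GEE models with treatment, time and their interaction, and adds covariates and confounders where thought necessary. It expects means, percentages and 95% intervals to help size the full-scale trial.

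The plan does not give an expected ICC or the number of therapy groups. It does not say whether the ICC is estimated within arm or over all groups, how group enters the model, or which degrees of freedom apply. The Selection Criteria and Treatment Fidelity paragraphs promise to look at therapist effects, but do not tie this to the between-arm tests.

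**The concern.** The plan recognises that people treated together may resemble one another, but lets an estimate from very few groups decide whether to allow for it. Three things follow.

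- An ICC at the threshold is not negligible. With 8 per group it inflates the variance of an arm difference by 1.7.
- Where the screen wrongly drops group, the test treats participants as independent and its interval is too narrow. Where the screen keeps group, the test is valid or cautious. The mixture has no guaranteed error rate.
- If the ICC is computed over all groups regardless of arm, the difference between arms counts as between-group variation. The treatment effect then helps decide how it is itself tested.

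At stake are the Aim 3 treatment and treatment-by-time tests and the intervals around arm means and differences. A group-delivered full-scale trial also needs the ICC as a planning input. The plan uses it only as a switch and does not promise to report it.

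**Working it through.** **Inputs.** From the plan: 64 randomised, equal allocation in blocks of 4 (so about 32 per arm), groups of 8–10, threshold 0.10, d = .72, two-sided 5%, 80% power, and 70% retention through follow-up (Table 5). Assumed, because the plan gives no value: true ICC from 0 to 0.20.

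**The plan's own figure.** For 32 per arm and a two-sample t test on 62 df, power at d = .72 is 81%, and 80% power is reached at d = 0.71. The stated .72 reproduces. It assumes 64 independent, fully observed participants.

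**Number of groups.** 64/8 = 8 and 64/10 = 6.4, so about 6 to 8. Three groups of 10 hold 30 of the 32 in an arm, so four groups of 8 per arm is the main case and three of 10 the alternative.

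**Design effect,** DE = 1 + (m − 1) × ICC, at ICC 0.10:
- m = 8: 1 + 7 × 0.10 = 1.70. Unadjusted intervals are too narrow by 1 − 1/√1.70 = 23%.
- m = 8 × 0.70 = 5.6: 1 + 4.6 × 0.10 = 1.46. Too narrow by 1 − 1/√1.46 = 17%.

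**How noisy the screen is** (four groups of 8 per arm, ANOVA ICC within arm, 6 and 56 df). The estimate is (F − 1)/(F + 7), so it exceeds 0.10 when F > 1 + 8 × 0.10/0.90 = 1.889. F is distributed as [1 + 8 × ICC/(1 − ICC)] times a central F(6, 56). At a true ICC of 0.10 that multiplier is also 1.889, so group is dropped with probability P(F(6, 56) < 1) = 56.5%. The central 95% of estimates runs from about −0.08 to 0.33.

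**Type I error of the screened procedure.** Simulated under no treatment effect, one outcome at one time. If the estimated ICC is 0.10 or less, participants are compared as independent. Otherwise arms are compared against between-group variation. Small-sample df means t on (participants − 2) or (groups − 2) df; z means 1.96 in both branches.

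| Groups per arm × analysed per group | True ICC | ICC estimated | Small-sample df | z |
|---|---|---|---|---|
| 4 × 8 | 0 | within arm | 4.5% | |
| 4 × 8 | 0.02 | within arm | 5.6% | |
| 4 × 8 | 0.05 | within arm | 7.0% | |
| 4 × 8 | 0.10 | within arm | 8.2% | 9.5% |
| 4 × 8 | 0.20 | within arm | 8.0% | |
| 4 × 6 | 0.10 | within arm | 6.9% | 8.3% |
| 4 × 5 | 0.10 | within arm | 6.1% | |
| 3 × 10 | 0.10 | within arm | about 9.5% | |
| 4 × 8 | 0.10 | pooled | 5.9% | 8.3% |
| 4 × 6 | 0.10 | pooled | 4.9% | 7.4% |
| 4 × 5 | 0.10 | pooled | 4.4% | |

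At ICC 0.10 with 4 × 8, always testing against group variation on 6 df gives 5.0%. Never modelling group gives about 14%.

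**Other outcome types,** 4 × 8, ICC 0.10 within arm: binary abstinence at 20–30% gives 7.6–9.0%. A five-visit AR(1) structure with complete data gives 6.7–8.8% when the group test uses 6 df.

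**Pooled estimation with a real effect.** At true ICC 0, the screen triggers adjustment in 9% of trials at d = 0 and in 57% at d = .72. At ICC 0.10 and d = .72, 95% intervals cover 92.8% of the time (90.0% with z).

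**The case against.** The strongest reply has four parts.

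- **The larger figures need conditions the plan does not state.** A reader might infer that Aim 3 tests simply run at 8–9% instead of 5%. The documents do not support that: it takes a true ICC of 0.10, within-arm estimation and no attrition together. At small ICCs, after the expected attrition, or with a pooled ICC and t tests, error is near or below nominal. This stands, and is why the size is given as a range.
- **Little depends on these tests.** The Study 2 primary outcomes are the Table 5 benchmarks. Aim 3 is declared descriptive and underpowered, its reading of benefit rests on within-participant change, and no decision uses a between-arm p-value. This also stands. A reader who inferred that the feasibility conclusions are unsafe would be wrong.
- **Clustering is not ignored.** The plan names the right unit and commits to estimating an ICC. True, so the fault is a poor rule rather than an omission. But nothing elsewhere in the plan ensures that group enters each between-arm comparison.
- **Always adjusting costs precision in a 64-person study.** This is correct. Showing the participant-level analysis alongside answers it in part.

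Pooling the ICC does not rescue the rule. It lowers the null error but makes adjustment depend on the treatment effect.

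**Conclusion.** The concern holds at moderate size. A 0.10 screen on about 6 to 8 groups cannot reliably tell whether clustering matters, and the plan leaves open the choices that fix its error rate. Over the settings tabulated, between-arm type I error is roughly 4–10%. Unadjusted 95% intervals at ICC 0.10 are 17–23% too narrow.

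These figures rest on an assumed ICC, a group count inferred from the stated group sizes, equal groups, and (for the main table) a single outcome at one visit. No repeated-measures result with the planned attrition was computed. At an ICC of 0.02 or less, error stays close to 5% with small-sample df.

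The point is worth fixing before analysis because the plan promises treatment-difference analyses and intends its intervals to inform the full-scale trial. It does not threaten the primary feasibility outcomes.

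**What to change.** **Change to make**

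- Delete the 0.10 threshold. Account for therapy group, nested in arm, in every between-arm Aim 3 analysis. Use either a comparison of group means or GEE clustered on therapy group with a bias-corrected sandwich variance, with a t reference on (groups − 2) df.
- A random group effect is an alternative only if negative variance estimates are allowed. Bounded at zero and tested on 6 df, it is conservative (about 3.3% at ICC 0.10, 1.2% at ICC 0), so it is not equivalent.
- Do not use a fixed group covariate, which is confounded with arm, or an uncorrected group-level sandwich, which runs at about 14% with eight clusters.
- Report the within-arm ICC with its confidence interval for each outcome, as input to the full-scale trial. The participant-level analysis may be shown as a sensitivity analysis.
- State that d = .72 assumes 64 independent, fully observed participants. Add the group-level detectable d for eight groups (6 df, 80% power): 0.84 with no loss and ICC 0; 1.01 with 70% retained and ICC 0; 1.10 with no loss and ICC 0.10; 1.22 with both.

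**Cost**

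No extra participants or visits. Group membership must be in the dataset. With group as the cluster, the planned AR(1) can hold only within participant, or working independence is used. If the true ICC is zero, intervals widen by about 22% (t of 2.447 on 6 df against 1.999 on 62 df), and power at d = .72 falls from about 81% to 67%. At ICC 0.10 that power is about 46%.
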